A small-scale two-group randomized controlled (RCT) pilot study of 28 African American female caregivers, age 40 and older with hypertension, will be conducted. We will determine the feasibility and acceptability of Mindfulness in Motion (MIM) plus the Dietary Approaches to Stop Hypertension (DASH). Participants will be randomized to either the MIM DASH intervention or the Alzheimer's Association Caregiver Training (attention control) delivered in 8 weekly, 1-hour group sessions via telehealth (video and telephone access). After completion of the intervention, both groups will receive eight weekly and then four monthly coaching calls or surveys through Mosio over the 9 months. To our knowledge, this is the first study that a) systematically employs one of the **Science of Behavioral Change key mechanisms underlying successful adoption** of health behaviors—stress reactivity/stress resilience and b) focuses solely on African American female caregivers of people living with dementia. The study aims are to:

AlM 1. Determine the feasibility and acceptability of MIM DASH and Caregiver Training for African American female caregivers with hypertension. Hypothesis: MIM DASH and Caregiver Training groups will be feasible and acceptable to caregivers. Method: We will track *feasibility*: screening to enrollment, attendance, attrition, completion of data collection procedures; and *acceptability*: treatment-specific preference ratings (prepost intervention). The Credibility Scale will capture attitudes towards the treatment condition and the participants' expectation of benefit once the treatment has been explained. Analysis: Feasibility and acceptability will be examined through descriptive statistics.

AIM 2. Explore the impact of MIM DASH as compared to Caregiving Training on caregiver stress and QOL. Hypothesis: MIM DASH group will have improved caregiver stress and QOL as compared to the Caregiver Training group. Method: The Perceived Stress Scale will be used as a measure of *caregiver stress* and the level of cortisol extracted from hair will be a proxy measure of *chronic stress*. The World Health Organization-5 will be used to measure QOL. The data will be collected in person and documented in REDCap at baseline, 3, and 9 months post-intervention. Analysis: We will conduct intent-to treat analysis and the fixed effect of MIM DASH intervention will be examined by mixed effects models.

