The **data collection** measures will be administered in both groups at baseline, 3, and 9 months. The study team will attempt to collect data within 8 weeks of the anticipated study visit dates. Data collection will take no longer than 120 minutes for each data collection session. Data collection will take place in the setting that is most convenient for the participant. For example, home or at the College of Nursing. Participant demographics and comorbidities will be collected at baseline. All other measures will be collected at baseline to 3, and 9 months as listed in Table 1. To accommodate the participants, who are caregivers, we will have the option for the study visits to be broken up into smaller 1 hour visits. Additionally, data that does not require an in person visit, such as questionnaires/surveys may be completed via phone or Zoom.

At baseline, we will administer the 6-item Newest Vital Sign as to measure health literacy. The Newest Vital Sign has high internal consistency (Cronbach's Alpha = 0.74). Validation against the Test of Functional Health Literacy in Adults demonstrated a Pearson's r of 0.49 and an area under the ROC curve of 0.81 (Table 1). Scores range from 0-6 with lower scores indicating lower health literacy.

For feasibility of recruitment, we will track the number screened per month; number eligible; number enrolled per month; average time delay from screening to enrollment; and the completion of data collection.⁵⁶ For acceptability, we will track treatment-specific preference ratings (pre- and post-intervention). For acceptability, we will track treatment-specific preference ratings (pre- and post-intervention). The participants will complete

IRB Approval date:

Version: 08/08/2023

10/05/2022

the Acceptability of Participant Preferences 13-item Likert-type survey ranging from 1 (strongly disagree) to 5 (strongly agree). Interventionists will keep detailed intervention session records describing participant response to the intervention. For the MIM DASH group, we will collect data regarding usage of self-care equipment (home BP monitor and MyPlate) from follow-up calls or surveys. We will use a credibility scale for both groups regarding the expectation of benefits of the study. The *Credibility Scale* (α = 0.86) measures attitudes towards the treatment condition and the participants' expectation of benefit once the treatment has been explained. ^{59,60}

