Consent forms will be stored in REDCap. Participant lists (ID number and demographic information) will be stored in the College of Nursing R:Drive on a spread sheet. The PI and designated study staff will have access to data. All participant data collected via REDCap will be labeled only with a code number. These coded data will be kept separate from the master list that links participants to their consent forms. Only the PI and designated research study staff will have access to the data.

IRB Approval date:

Version: 08/08/2023

10/05/2022

This study will utilize REDCap (Research Electronic Data Capture), a software toolset and workflow methodology for electronic collection and management of clinical and research data, to collect and store data. The OSU Center for Clinical and Translational Science (CCTS) Research Informatics Services will be used as a central location for data processing and management. REDCap provides a secure, web-based application that provides an intuitive data manipulation interface, custom reporting capabilities, audit trail functionality, real-time data monitoring/querying of participant records, and variations of data exporting/importing. REDCap is hosted by OSUWMC IT in the Ackerman Datacenter ([name])

REDCap instance is located on internal OSUWMC network. Remote access to this network can be obtained over an encrypted VPN tunnel (AnyConnect) This VPN uses Protocol: DTLS and Cipher: RSA_AES_128_SHA1. Background checks are performed on all staff that are on the network or obtaining VPN access.

Termination for Significant Risk: Although the study is deemed low risk and adverse events are not anticipated, diligent monitoring will occur as specified above under Adverse Events Protocols. A participant that expresses concern about his or her participation or reports distress associated with receiving the intervention may be asked to discontinue participation in the study if there is concern about participant safety and wellbeing or about the safety and wellbeing of others. Likewise, if one of the research assistants, interventionists or supervising members of the Research Team expresses a concern about a participant's safety or wellbeing, the Office of Responsible Research Practices Adverse Events Reporting process will be used and it is possible that the participant could be asked to discontinue participation if there were concern about his or her, or others, safety and wellbeing.

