Protection of Privacy. For all potential participants, the data collection interviews will take place in a private room with closed door. All research team members will be certified with The Ohio State University (OSU) IRB, HIPAA, and CITI training. Careful training and supervision of all study staff will ensure procedures are carried out in accordance with established protocols. Timely team meetings (at least twice monthly) will be conducted to evaluate consent procedures, study data collections, and other study activities to ensure consistency with planned study procedures. Should an adverse event occur, PI [name] will report this to the OSU IRB.

Protection of Confidentiality. Study staff will be carefully trained to protect participant confidentiality. They will work with participants to devise a plan for contacting them by phone, email, text messaging, or some other means determined by the participant, and decide whether or not messages may be left. Participants will be assigned a study identification number, and a master log will be created associating participant names and study number. The master log will be stored separately from data in the CON R: Drive folder. Only the PI and designated study staff will have access to the master log, and the master log will be destroyed at the end of the study. Study staff access to study data will be determined based on the relevance to their responsibilities. Only aggregate data will be reported for the dissemination of study findings.

Consents and any other forms with identifiable subject information will be maintained in a locked file separate from the filed study data which will be identified only by subject numbers. Data from questionnaires will be entered into REDCap. Destruction of paper logs and forms will follow OSU protocols. Findings will be reported in a manner in which individual data for specific participants are not identifiable.

To mitigate the risk that participants violate the privacy and confidentiality of others in their group sessions, we will ask that those participants (and their family/support person) refrain from discussing other participants outside the group. Likewise, they will be asked not to acknowledge having met if they encounter each other elsewhere. These steps are not foolproof, and participants will be informed of the associated risks at the time of consent.

IRB Approval date:

Version: 08/08/2023

10/05/2022

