The study is a RCT with equal attention for both conditions. We will repeat surveys measures over three time points (baseline, 1 month, 9 months) to reduce regression to the mean as an internal validity threat. We have also employed strategies to improve participant retention.

Retention. Participants will be enrolled for 9 months. We anticipate low drop out during this time. However, should a participant drop out for any reason (illness, refusal, etc.), then additional participants will be enrolled to maintain sample size. In studies longitudinal studies, a threat to internal validity is selection bias or selection threat. This can occur due to study drop out. To decrease the risk of participants dropping out of the study, we have employed several strategies.

- a. Data collection and intervention delivery option for weekends and evenings.
- b. Intervention delivery option for weekends and evenings.
- c. Reminder calls to participants for data collection and sessions.
- d. Participants will also receive a home blood pressure monitor and a MyPlate depicting a well-balanced diet of protein, fruit/vegetables, and carbohydrates.
- e. Free parking or round trip transportation is provided for data collection.
- f. With permission from the participant, we will send text messages, emails, and or phone call reminders for visits.
- g. Incentives include \$50 cash given to participants at each data collection point (baseline, 3 and 9 months).
- h. Data collectors will be available to go to the participant's preferred location if they do not want to come to the College of Nursing.

IRB Approval date:

Version: 08/08/2023

10/05/2022

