Since participants may have a wait before baseline data are collected and the start of the group sessions, we have several incentives. We will send reminder greeting cards, postcards, and unexpected token gifts (each valued at under \$7, e.g., water bottle, cinch bag) to participants. In our experience, participants bond to such staff and remain in studies to a large degree because of the personal relationships and trust; a key component to working with the African American community. PI [name] has established community relationships with key stakeholders including the American Heart Association, Franklin County, Franklin County Hypertension Network, and local churches. If an increase in missed visits occurs, the PI and the project coordinator will review with the RAs the root cause for the missed visits and review procedures for contacting participants.

[name] will monitor any adverse events that arise in the course of the study. Any adverse events will be reported in writing to Ohio State University IRB. The PI will stop any data collection for the aim in which there has been an adverse effect until the adverse effect is resolved. A Safety Officer will be appointed to provide oversight of data collection and analyses. If the needs arise, a data safety and monitoring board will be formed. Given the low risks associated with lighting intervention (non-pharmacological education intervention), we do not foresee a need for a DSMB, but we will be working with a Safety Officer who can provide independent oversight of the project.

DATA ANALYSIS

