Aim 1. Analysis. We will conduct descriptive data analyses to check data accuracy, summarize participant characteristics, and examine variable distributions. Data anomalies once identified will be fully investigated and remedial strategies will be considered as appropriate. We will use descriptive statistics to examine the feasibility and acceptability of the MIM DASH intervention and Caregiver Training, including a) approach-to-enrollment ratio; b) proportion of participants that complete all eight sessions of assigned intervention arm and attention control arm; c) frequency of completion of the follow-up calls or surveys; d) proportion of days the study protocol is fully adhered to and proportion of protocol deviation among interventionists; e) mean rating of MIM DASH intervention; and f) proportion of participants rating the MIM DASH intervention positively (4 or above). We will report point estimates along with 95% confidence intervals to indicate the precision of the estimates. Based on our experience enrolling African American participants in studies, feasibility will be defined by: a) enrolling at least 40% of potentially eligible patients and b) completion of at least 75% of the assigned intervention. Acceptability will be defined by an average rating of 4 and at least 80% participants rating the intervention positively.

Aim 2 Analysis. We will conduct intent-to treat analysis. Descriptive statistics including mean and standard deviation will be used to summarize each primary outcome and secondary outcome. We will also report mean differences, 95% confidences intervals, and effect sizes for both within- and between-group differences at each visit. The fixed effect of MIM DASH intervention will be examined by mixed effects models

Aim 3 Analysis. We will conduct mediation analysis for both groups. Each variable will be first summarized by descriptive statistics. Then we will examine the mediation effects of stress reactivity/stress resilience between the MIM DASH intervention or Caregiver Training and behavior change. The estimated mediation effects and 95% confidence intervals will be reported

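### A woman asked to stop because of distress or a safety concern leaves the whole study, and no available text keeps her stress and quality-of-life scores coming, so unbalanced early removals could flatter an arm in the exploratory Aim 2 comparison

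*Combined protocol and SAP*

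**What the plan says.** The protocol has two routes to removal, both under Termination for Significant Risk. In the first, the participant voices concern, or she "reports distress associated with receiving the intervention may be asked to discontinue participation in the study if there is concern about participant safety and wellbeing". In the second, a member of the research team raises the concern; then "it is possible that the participant could be asked to discontinue participation if there were concern about his or her, or others, safety and wellbeing". Neither route distinguishes stopping the sessions from leaving the study.

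Other sections bear on what follows:

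- **Protection against Psychological Harm** gives a first response to visible discomfort: a quiet area, support, and notifying the principal investigator. This is care, not outcome follow-up.
- **Internal Validity, Retention:** "should a participant drop out for any reason (illness, refusal, etc.), then additional participants will be enrolled to maintain sample size".
- **Adverse-event paragraph before Data Analysis:** "The PI will stop any data collection for the aim in which there has been an adverse effect until the adverse effect is resolved".
- **Measurement/Instrumentation** schedules PSS and WHO-5 at baseline, 3 and 9 months, with an 8-week visit window, and allows that "data that does not require an in person visit, such as questionnaires/surveys may be completed via phone or Zoom". It does not mention women who have stopped.
- **Aim 1** tracks "screening to enrollment, attendance, attrition, completion of data collection procedures".
- **Aim 2 Analysis** names intent-to-treat and mixed effects models and promises "effect sizes for both within- and between-group differences at each visit". It gives no missing-data assumption and no sensitivity analysis.

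**The concern.** Most dropout in a caregiver study has causes only loosely tied to the outcome. Here the plan itself can end a woman's participation because the intervention distresses her, and Aim 2 measures stress and wellbeing. Her missing scores would probably have been worse than average for her arm.

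A likelihood-based mixed model copes with missing scores when the missingness is explained by scores already observed. Distress that arises during the sessions is not in the baseline score. If baseline is all she has, the model predicts her later course from women who stayed, and her worsening disappears from the estimate.

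If this happens more in one arm, that arm looks better than it was. The background section says the findings will lead to a larger randomised trial, so both the effect size and the picture of tolerability carry forward. Aim 1 tracks total attrition, but discontinuation for distress by arm is not among the listed summaries.

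**Working it through.** **The plan's own figure.** The Sampling Plan gives 28 women including 28.6% for attrition. With 20 completers (inferred, not stated), 20/(1 − 0.286) = 28.0 and 8/28 = 28.6%, so the figure reproduces. It covers attrition for any reason. No expected number of distress removals, SD or power figure is given.

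**Assumptions.** 14 per arm (no allocation ratio is stated); k = 1 to 3 more removals in one arm than the other; each removed woman would have scored d = 1 to 2 SD worse; correlation between visits r = 0.6.

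**Step 1: removal before any post-baseline score.** The arm mean loses k women who were each d worse, so shift = k·d/14. If later enrollees are additional, the full arm has 14 + k women and shift = k·d/(14 + k).

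| k | d | k·d/14 | k·d/(14 + k) |
|---|---|---|---|
| 1 | 1 | 0.071 | 0.067 |
| 1 | 2 | 0.143 | 0.133 |
| 2 | 1 | 0.143 | 0.125 |
| 2 | 2 | 0.286 | 0.250 |
| 3 | 1 | 0.214 | 0.176 |
| 3 | 2 | 0.429 | 0.353 |

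In points, with 14 per arm: PSS (SD assumed 5 to 7) 5 × 1/14 = 0.4 to 7 × 6/14 = 3.0; WHO-5 (SD assumed 4 to 6) 4 × 1/14 = 0.3 to 6 × 6/14 = 2.6.

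**Step 2: removal after the 3-month visit, with the worsening already visible.** The 3-month result is complete. At 9 months a random-intercept model recovers r/(1 + r) = 0.6/1.6 = 0.375 of the shift, leaving 0.625·k·d/14 = 0.04 to 0.27 SD.

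**Step 3: precision.** For change from baseline, SE = √(2 × 2(1 − r)/14) = √(2 × 0.8/14) = 0.338 SD, and 1.96 × 0.338 = 0.66 SD. The largest shift, 0.43, is inside that.

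**Step 4: simulation of the mixed model** (three visits, 2,000 replicates, smallest to largest case). The mean arm difference at 9 months was 0.07 to 0.42 SD with full follow-up, about 0 (−0.02 to 0.01) with removal before 3 months, replaced or not, and 0.02 to 0.16 with removal after 3 months. Early removal therefore erases essentially all of the added harm. Replacement changes only the SE (0.335 to 0.337, against 0.343 to 0.356 without it).

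**Step 5: a second mechanism.** Here the most distressed women in one arm were removed before 3 months and PSS was adjusted for baseline (SD 6, r = 0.6, no true difference). With 1, 2 or 4 of 14 removed, the bias was −0.6, −1.2 and −2.1 points when removal followed the unseen score fully, and −0.3, −0.6 and −1.1 when the link was half as strong. With no scores lost, it was zero.

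**Step 6: timing.** The aims count months from the end of the intervention; Measurement/Instrumentation does not say. Counted from the end of the intervention, a woman removed during the sessions has baseline scores only. Counted from baseline, this is not certain: three months is about 13 weeks, the sessions take 8, and the Retention section allows for a wait before the groups start. A wait of about 5 weeks (13 − 8) or use of the 8-week window could put the 3-month visit inside the session period. Step 2 is then the relevant case for some women.

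**The case against.** The strongest reply is that the trigger is narrow. It sits under a heading about significant risk, it says a woman may be asked, it requires a safety or wellbeing concern, and the study is described as low risk. Nothing in the documents suggests an excess of 1 to 3 removals in one arm. That stands, and the sizes above are conditional on it. Still, with 14 per arm one woman is 7% of the arm.

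Second, ordinary attrition is the larger missing-data problem: 28.6% is planned for and the earlier MIM DASH trial lost 50%. That is fair. Removal for distress deserves its own rule because the plan initiates the loss and the reason is close to the outcome.

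Third, some safeguards exist. Data completion is logged for each participant, and a Safety Officer oversees data collection and analyses. Neither supplies scores after removal or counts removals for distress by arm.

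Fourth, terms on data after withdrawal may be in the consent pages, which were not available. The termination section also refers to adverse-event procedures that do not appear in the supplied text. This limits the claim of absence.

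A reader might infer more than the documents support:

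- *That removed women are dropped from the analysis and swapped for others.* Intent-to-treat in its ordinary meaning keeps each woman in her assigned arm, and the Retention section calls later enrollees additional.
- *That replacement causes the bias.* It does not (Step 4); it can only mask the loss of numbers.
- *That the pause after an adverse effect tilts the comparison.* It applies to an aim, not to an arm.
- *That a false positive is likely.* Aim 2 is exploratory, and every case lies within the confidence interval.

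**Conclusion.** The point holds in a limited form. As written, removal for distress or safety ends study participation, and no available section preserves later PSS and WHO-5 scores. The intent-to-treat label does not supply those scores, and a mixed model with only a baseline value cannot recover them.

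The consequence is a possible directional shift in an exploratory estimate. It needs removals to be unequal between arms and the removed women to be truly worse. Under the stated assumptions it is 0.07 to 0.43 SD if they leave before a 3-month score, and 0.04 to 0.27 SD at 9 months if they leave afterwards. The true size is unknown. The change is worth making because it is cheap and scores not collected at the time cannot be obtained later.

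**What to change.** **Termination for Significant Risk.** State that a woman asked to stop, by either route, stops the intervention and any study procedure judged unsafe for her (the Pittsburgh Stress Battery, for example). With her agreement, PSS and WHO-5 are still collected at 3 and 9 months by phone or Zoom, within the existing 8-week window where possible. If collection for the aim is paused at her visit date, they are taken when the pause ends.

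**Data Analysis, Aim 2.** State that every randomised woman is analysed in her assigned arm and that women enrolled after a dropout are additional. Report by arm the number discontinued for distress or safety and the number with missing scores. Counts are enough, in keeping with the confidentiality rule that "Only aggregate data will be reported for the dissemination of study findings".

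**Sensitivity analysis, if one is added.** Use multiple imputation with a delta shift, for example 1 SD and then 2 SD worse. Apply it only to the missing visits of women removed for distress or safety, including those who leave after 3 months. A fixed worse value for every dropout would be wrong: two extra ordinary dropouts in one arm would move the estimate 2 × 1/14 = 0.14 to 2 × 2/14 = 0.29 SD against it, and a single value would understate the uncertainty.

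**Cost.** A few sentences in two sections, at most two phone contacts per woman who stops, and a protocol (possibly consent) amendment. Some scores will still be missing where a woman declines.

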Sampling Plan. Our prior work in hypertensive African Americans demonstrates that we can enroll N=28 caregivers. The total enrollment includes 28.6% oversampling to account for attrition. The composition of Blacks in the Columbus area is representative of the United States population at 22.86%. Forty-seven percent of Blacks in Ohio have hypertension. Most of the potential participants will be recruited from the African American Alzheimer's and Wellness Center—sampling frame of 242 middle-aged African American women. From prior experience, we do not anticipate difficulty recruiting participants for this study.

Eligibility Criteria: Inclusion criteria are (1) diagnosis of HTN treated with an antihypertensive medication or risk of HTN that includes obesity and high cholesterol; (2) age 40 and older (3) a caregiver rating of the PLWD of 2 or greater on the Alzheimer's Dementia-8 scale; (4) caregiver provides unpaid care to a PLWD at least 10 hours per week or assists with at least one instrumental activity of daily living (5) self-identifies as Black/African American; (6) English speaking; and (7) access to a telecommunications device such as the internet via desktop, laptop/tablet, smartphone, or telephone. Exclusion criteria are (1) expect to move out of the area within 9 months; (2) diagnosis of resistant HTN (blood pressure that remains above goal despite concurrent use of a diuretic/water pill and at least two other antihypertensive agents of different classes); or (3) active participation in mindfulness/yoga program. The NIA Common Data Screening and Enrollment forms will be used to track data.

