sessions and support the adoption of self-care behaviors. Our team has experience in delivering the MIM DASH intervention for older African Americans with hypertension.

Caregiver Training-Attention Control. A trained interventionist will deliver the Caregiver Training. Participants in this group will attend eight 1-hour group lessons via telehealth for 8 weeks. We will use Alzheimer's Association caregiver training resources on topics such as Healthy Living for Your Brain and Body: Tips from the Latest Research; Dementia Conversations: Driving, Doctors Visits, Legal and Financial Planning; and Understanding and Responding to Dementia-Related Behavior. Similar to the MIM DASH group, participants will receive educational materials so they can follow along using videoconferencing or phone. Participants will have group discussion and role play using case study scenario. They will receive eight weekly and then four monthly social calls to maintain participants' involvement and enhance participant retention. Our team has experience working with attention control groups for African Americans. At the end of the study, the Caregiver Training group will receive a home BP monitor, a MyPlate, and American Heart Association home BP infographic and video. They will also have the opportunity to receive a short video describing MIM DASH after the study ends. The MIM DASH group will receive instead the Caregiver Training materials.

There will be additional short video and educational materials for MIM DASH and Caregiver Training will be submitted as an amendment for IRB approval prior to participants viewing materials.

The participant can enter Zoom sessions by invitation only. If the participant does not have access to a touch screen tablet or computer, they may be able to borrow an iPads from the College of Nursing. This would be mailed to the participant with return postage paid.

- 1. Meetings will require a password by default. These passwords will be embedded in the meeting URL (link) by default.
- 2. Annotations will not be available to participants by default.
- The ability to join a meeting before the host or alternate host joins will be disabled by default
- 4. Participants will not be able to change their names by default.

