Participant protection and Zoom. Using the **Only authenticated** users can join setting will prevent guests who do not have an Ohio State Zoom account from entering the session. Since the meeting includes non-university participants, the PI will use the following strategies to control who can attend.

- ♣ Participants only with access can join
- Turn off the option to Join before Host
- ♣ Turn on the Waiting Room
- Meeting will be password protected

Participants will be encouraged to use their camera to facilitate interaction. However, participants will be a given the choice to turn off their camera and microphone and use the Zoom Chat if they prefer. Participants may use an avatar image of themselves in the Zoom room. Each cohort will chose a pseudonym for their cohort. Participants may share their contact information, not required, if they would like to support one another in their health goals. The study staff will not provide participants with each other's' contact information.

Field Notes

Research staff may describe their thoughts about factors they observed that contributed to the quality of each encounter by writing a brief field note. The field notes will be documented in REDCap. A descriptive qualitative analysis will be conducted to categorize themes.

IRB Approval date:

Version: 08/08/2023

10/05/2022

Intervention fidelity (Table 2) will be evaluated to provide assurance that MIM DASH and Caregiver Training are implemented as intended and will assure reproducibility of the protocol. The MIM DASH group will receive the Caregiver Training materials at the conclusion of the study.

Component	Data used to Evaluate Intervention Fidelity	Table 2. Intervention Fidelity		
Design	Detailed protocol manual for intervention sessions and common problem areas and weekly review of interventionist field notes.			
Training	Research Staff Training: Pre-study simulations and observed data collection. Data collection accuracy at start-up and maintenance			
	will be >.90. Interventionist Training: Each interventionist will complete training to competence under the supervision of PI [name] and			
	Co-l's [name], and [name]. All training will be video-recorded with feedback provided and corrected performance observed.			
Delivery	Delivery of Intervention: Field notes will be recorded for all sessions as evidence of completion and to document barriers and facilitators			

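### Both arms are taught in interacting session groups, but the Aim 2 analysis makes no allowance for session group; if groups are ignored and outcomes correlate within them, the between-arm 95% intervals will be too narrow

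*Combined protocol and SAP*

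**What the plan says.** The Introduction describes "A small-scale two-group randomized controlled (RCT) pilot study of 28 African American female caregivers". Individuals are randomized, and each arm is delivered as eight weekly one-hour telehealth group sessions.

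Interaction is part of the design. The MIM DASH Intervention section has participants exchange ideas on practice and daily difficulties. The Caregiver Training section says "Participants in this group will attend eight 1-hour group lessons via telehealth for 8 weeks" and adds discussion and role play. Under Participant protection and Zoom, "Each cohort will chose a pseudonym for their cohort", and "Participants may share their contact information, not required, if they would like to support one another in their health goals".

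The Aim 2 paragraph of Data Analysis specifies intent-to-treat analysis, then mean differences, 95% confidence intervals and effect sizes within and between groups at each visit. The model itself gets one sentence: "The fixed effect of MIM DASH intervention will be examined by mixed effects models". No random effect is named, not even one for participant. Session group, cohort, interventionist, ICC and design effect appear in neither the Sampling Plan nor Data Analysis. The number and size of the cohorts are not stated. The tracking described under Recruitment (in the data-integrity text) covers participation but does not mention a session-group identifier.

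**The concern.** Women in one session group share a facilitator, a timetable and each other's support for eight weeks. The plan's own framework expects this to matter: Preliminary Work lists group support as a facilitator of self-care and builds motivation on a supportive social setting. Some positive correlation of outcomes within a group is therefore plausible.

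An analysis that treats the women as independent would then understate the standard error of the between-arm difference. A random intercept for participant would not repair this, because it handles repeated visits by one woman and not similarity between women. In an exploratory pilot the interval is the main protection against over-reading a chance difference in stress or quality of life. If group membership is not recorded, no correction can be made afterwards.

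**Working it through.** **Inputs from the documents.** Total 28 in two arms (Introduction). Attrition allowance: "The total enrollment includes 28.6% oversampling to account for attrition" (Sampling Plan).

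**Assumed, because the documents are silent.** 1:1 allocation (14 per arm); one or two session groups per arm; ICC 0.01, 0.05 or 0.10.

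**The plan's own figure.** 28 × (1 − 0.286) = 19.99, so about 20 completers, or 10 per arm. In reverse, 20 / (1 − 0.286) = 28.01, which matches 28. The base of 20 is inferred. Nothing in this arithmetic allows for clustering. The Retention section also says that dropouts will be replaced, so both 14 and 10 per arm are shown.

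**Standard-error multiplier.** With groups of size m, the design effect is 1 + (m − 1) × ICC and the multiplier is its square root. For example:
- m = 7, ICC 0.05: sqrt(1 + 6 × 0.05) = sqrt(1.30) = 1.14
- m = 14, ICC 0.10: sqrt(1 + 13 × 0.10) = sqrt(2.30) = 1.52

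**Rejection rate of a nominal 5% test.** Null trials were simulated with a normal group effect and analysed by a two-sample t-test at one visit that ignores group. Each cell lists ICC 0.01 / 0.05 / 0.10.

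| Layout per arm | Multiplier | Rejection rate |
|---|---|---|
| Two groups of 7 | 1.03 / 1.14 / 1.26 | 5.7% / 8.7% / 12.5% |
| One group of 14 | 1.06 / 1.28 / 1.52 | 6.4% / 13.0% / 21.0% |
| Two groups of 5 (10 completers) | 1.02 / 1.10 / 1.18 | 5.3% / 7.3% / 10.2% |
| One group of 10 (10 completers) | 1.04 / 1.20 / 1.38 | 6.3% / 10.6% / 16.7% |

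At ICC 0 the rate is 5%. Coverage of the 95% interval is 100% minus the rejection rate.

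**Exact check for one group per arm.** The naive SD then reflects only within-group variance, so the t statistic is inflated by sqrt((1 + (m − 1) × ICC) / (1 − ICC)). For m = 14 and ICC 0.10 this is sqrt(2.30 / 0.90) = 1.60. The rejection rate is P(|t| > 2.056 / 1.60) on 26 df = 21.0%, as simulated. The multiplier of 1.52 therefore slightly under-corrects: after it is applied, rejection is P(|t| > 2.056 × 1.52 / 1.60), about 6%.

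**A participant random intercept.** With the mean of two follow-up visits and an assumed within-person correlation of 0.5, simulated coverage at single-visit ICC 0.05 is 90.0% (two groups of 7) and 83.9% (one group of 14). Modelling the repeated visits does not remove the problem.

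**Can a group level be estimated?** With one group per arm the group effect is confounded with treatment (0 df). With two per arm there are 4 − 2 = 2 df. The unadjusted half-width is 2.056 × sqrt(2/14) = 0.78 SD. With 2 df and ICC 0.05 it becomes 4.303 × sqrt(2/14) × 1.14 = 1.85 SD, too wide to be useful.

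**The case against.** A reader might infer that the Aim 2 model excludes session group and that its intervals are too narrow as a matter of fact. The documents support neither. The whole random-effects structure is left open, so a group level is unspecified and not shown to be ruled out. Under-coverage also needs a positive ICC, and none is given. At ICC 0.01 with groups of 5 or 7 the loss is negligible. This objection stands, and the point is worded conditionally for that reason.

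A reader might also infer that Aim 2 effect sizes will set the design of the next trial. The Introduction says only that findings will inform the infrastructure for a larger trial. Aim 2 is framed as exploration; the numerical success criteria belong to Aim 1. No significance test is specified for Aim 2, so the rejection rates are best read as lost interval coverage. The interval is wide anyway: 0.78 SD unadjusted against 0.78 × 1.14 = 0.89 SD with two groups of 7 at ICC 0.05. This limits the consequence but does not excuse the silence, because between-group 95% intervals are promised at each visit.

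The largest figures need ICC 0.10, a single group of 14 per arm and no loss to follow-up. That is the extreme corner of the range, not an expectation.

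**Conclusion.** The concern holds in conditional form. Both arms meet in interacting groups, and the Aim 2 plan neither names random effects nor allows for session group. If groups are ignored and the ICC is positive, the between-arm 95% intervals under-cover. Over the assumed layouts and ICCs of 0.01 to 0.10, the actual error rate behind a nominal 5% runs from about 5.3% to 21.0%; at ICC 0 nothing is lost. These figures rest on assumed ICCs and group sizes, 1:1 allocation and a single-visit comparison. It is a gap worth closing in an exploratory analysis and does not invalidate the pilot.

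**What to change.** - Record a session-group ID for every participant, and report the number and size of groups in each arm.
- Name the random effects of the Aim 2 model.
- Beside each exploratory between-arm estimate, report a sensitivity interval with the standard error multiplied by sqrt(1 + (m − 1) × ICC), where m is the actual group size, at assumed ICCs of 0.01, 0.05 and 0.10. Say that the correction is approximate and that the ICC is that of the contrast being estimated.
- State that the unadjusted interval is conditional on these particular groups and facilitators.
- Do not rely on an estimated random group effect, which has 0 df with one group per arm and 2 df with two.

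The cost is one extra data field and a few lines of analysis text. Sample size and participant procedures do not change. The downside is that the sensitivity intervals are wider, by about 2% (two groups of 5, ICC 0.01) to 52% (one group of 14, ICC 0.10).
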